## 2 STUDY SYNOPSIS

**Name of Sponsor:** Investigator initiated – [name].

**Name of Product:** INVOS® 5100 Near Infra-Red Spectrophotometer (Covidien, Boulder, CO)

**Title of Study:** Near Infra-Red Spectrophotometry (NIRS)-Based Cerebral Oximetry Monitoring in Elderly Thoracic Surgical Patients Undergoing Single Lung Ventilation Procedures: A Single Center, Prospective, Randomized Controlled Pilot Study Assessing the Clinical Impact of NIRS-Guided Intervention

**Study Center:** University Hospitals Case Medical Center (UHCMC), Cleveland, OH – Case Western Reserve University School of Medicine (CWRUSOM)

### **Study Rationale**

The use of bi-frontal, near infrared spectrophotometry (NIRS) based cerebral oximetry monitoring has been demonstrated to result in improved clinical outcomes in both general surgery patients and cardiac surgical patients using prospective, randomized controlled trial methodology. Elderly thoracic surgical patients undergoing procedures that involve single lung ventilation may also stand to benefit from the application of intraoperative and early postoperative NIRS cerebral oximetry monitoring. Cerebral oximetry has not been established as a standard of care monitoring modality in this patient population, thus permitting the application of randomized, controlled testing methodology to assess the potential impact of this monitoring modality upon these patients.

### **Hypothesis and Objectives:**

The primary hypothesis in this pilot study of elderly thoracic surgical patients undergoing procedures involving single lung ventilation (SLV) is that there will be a measurable and significant clinical benefit (as assessed by a broad range of postoperative clinical outcome measures) to the subjects randomized to the intervention cohort (open bi-frontal NIRS based cerebral oximetry monitoring with a standardized intervention protocol) vs. the control cohort (blinded bi-frontal NIRS based cerebral oximetry monitoring).

The primary objective of this pilot study is to identify the most relevant clinical outcome variables which significantly diverge as a result of being randomized to the intervention cohort vs. the control cohort so that a larger, multicenter, prospective, randomized controlled clinical trial can be designed to further test the primary hypothesis as stated in the preceding section. The subsequent larger, multicenter trial will be conducted to definitively demonstrate the ability of INVOS® 5100 guided NIRS-based bi-frontal monitoring to improve clinical outcomes in this surgical patient group and potentially establish a new U.S. Food and Drug Administration cleared indication for this monitoring modality.

Secondary objectives of this pilot study include the following:

- 1) Assess the frequency of cerebral desaturations in both the intervention and control cohorts by examining both the total number of patients experiencing any cerebral desaturation as well as the total number of events among patients experiencing any cerebral desaturation (of at least 5% below

baseline and progressively larger desaturations). These analyses will be conducted on the entire study population as well as upon each cohort. The Area Under the Curve (AUC) analysis technique [incremental desaturation categories will be assessed based upon 5 to 50% decreases, measured in 5% increments, from established room air pre-incision baseline as well as oxygen supplemented preincision baseline as well as desaturations below absolute measured rSO2 values] will be employed to conduct these analyses.

- 2) Assess the frequency of adverse clinical events and serious adverse events overall and in each cohort.
- 3) Perform a comprehensive assessment of the frequency and efficacy of predefined rSO2 desaturation mitigation interventions and their collective ability to affect the observed cerebral oximetry values.
- 4) Assess the interventional cohort's preoperative demographics and collected covariates for association with the ease or difficulty of mitigating observed cerebral desaturation events.

Exploratory analyses will include performing all possible comparisons of the two groups based upon all collected perioperative variables to examine the potentially significant relationships between the collected clinical variables representing surrogates of organ perfusion/function and cerebral oximetry desaturations (AUCrSO2). The following exploratory endpoints will be assessed:

- Logistic regression analysis to determine the most relevant AUCrSO2 desaturation value(s) associated with any detrimental clinical outcome(s) monitored in this study
- Logistic regression analysis to determine the most relevant AUC blood pressure values associated with any detrimental clinical outcome(s) monitored in this study
- Comparison of baseline rSO2 values (room air and oxygen supplemented) to all collected clinical variables to assess for possibly significant associations
- Explore the potential impact of rSO2 monitoring on changing the surgical conduct of the procedure

**Methodology:** Single center, prospective, randomized, controlled clinical pilot study

**Number of Subjects:** 100 subjects with balanced randomization (1:1) to control (blinded NIRS data) or intervention (open NIRS data) cohorts

**Main Criteria for Inclusion:** Elderly patients (> 65 years of age) scheduled for a thoracic surgical procedure at UHCMC that will involve SLV.

**Duration of Treatment:** Cerebral oximetry monitoring will begin with an assessment of both room air and oxygen supplemented bi-frontal baseline NIRS values and continue through the surgery to either PACU discharge or the initial 12 hours of post surgical ICU treatment. Mini Mental Status exam testing and Delirium testing with the Confusion Assessment Method will occur preoperatively and postoperatively through post-operative day (POD) #3 (or discharge if that occurs sooner than POD #3).

Enrolled subjects will be followed during the index hospitalization and will undergo a 30 day follow up telephone interview to assess their progress following hospital discharge.

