### 7.2.3 Intraoperative and Immediate Postoperative Period

The intraoperative period will occur immediately following completion of the Baseline Acquisition Period. Subjects randomized to the control group will be induced into general anesthesia with electronically blinded rSO2 monitoring while those randomized to the intervention cohort will undergo open rSO2 monitoring with the application of a standardized interventional protocol (Appendix D) for any observed significant cerebral desaturations. Significant cerebral desaturations are defined as any desaturation  $\geq 10\%$  of established room air baseline values for each individual subject. This period will continue through the end of the surgical procedure to PACU discharge or if the subject goes to the ICU through the first 12 hours of ICU admission.

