## **Schematic Diagram of Trial Design**

## 7.4 Study Variables

### 7.4.1 Primary Endpoints

The relationship between the observed cerebral oximetry data and a number of predefined intraoperative and postoperative clinical variables will serve as the primary endpoints of this trial. The clinical variables will include the following intraoperative and postoperative (PACU or initial 12 hours of the ICU stay) parameters:

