#### 7.4.1.1 Intraoperative:

- Area under the curve of cumulative rSO2 desaturations (AUCrSO2) of progressive categorical degrees that will include the following:
  - < 5% of established room air baseline and oxygen supplemented baseline ○ < 10% of established room air baseline and oxygen supplemented baseline ○ < 15% of established room air baseline and oxygen supplemented baseline ○ < 20% of established room air baseline and oxygen supplemented baseline ○ < 25% of established room air baseline and oxygen supplemented baseline ○ < 30% of established room air baseline and oxygen supplemented baseline ○ < 35% of established room air baseline and oxygen supplemented baseline ○ < 40% of established room air baseline and oxygen supplemented baseline ○ < 60% of absolute measured value (if baseline > 60%) ○ < 55% of absolute measured value (if baseline > 55%) ○ < 50% of absolute measured value (if baseline > 50%) ○ < 45% of absolute measured value (if baseline > 45%) ○ < 40% of absolute measured value ○ < 35% of absolute measured value

○ < 30% of absolute measured value ○ < 25% of absolute

measured value ○ < 20% of absolute measured value

- Area under the curve for cumulative, high and low intraoperative values outside of preestablished, individualized patient blood pressure goals based upon preoperatively observed blood pressure values as well as values clinically accepted to provide adequate organ perfusion. This analysis will be performed for systolic, diastolic and mean arterial pressures (AUCSBP-hi, AUCSBP-low, AUCSBP-cum, AUCDBP-hi, AUCDBP-low, AUCDBP-cum, AUCMAP-hi, AUCMAP-low, AUCMAP-cum). All intraoperative pressure data will be collected with either invasive arterial catheterization [Q30 secs] or non-invasive blood pressure monitoring [Q3 min] as determined by the attending anesthesiologist caring for the subject.
- Area under the curve of intraoperative progressive categorical pulse oximetry (SpO2) desaturations (AUCSpO2) including the following:
  - AUCSpO2 < 95% regardless of intraoperative FiO2 values ○
  - AUCSpO2 < 90% regardless of intraoperative FiO2 values ○
  - AUCSpO2 < 85% regardless of intraoperative FiO2 values ○

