#### 7.4.1.2 Postoperative:

- ❶ Area under the curve of  $rSO_2$  desaturations ( $AUC_{rSO_2}$ ) of progressive categorical degrees that will include the following:
  - < 5% of established room air baseline and oxygen supplemented baseline ○ < 10% of established room air baseline and oxygen supplemented baseline ○ < 15% of established room air baseline and oxygen supplemented baseline ○ < 20% of established room air baseline and oxygen supplemented baseline ○ < 25% of established room air baseline and oxygen supplemented baseline ○ < 30% of established room air baseline and oxygen supplemented baseline

baseline ○ < 35% of established room air baseline and oxygen

supplemented baseline ○ < 40% of established room air

baseline and oxygen supplemented baseline ○ < 60% of

absolute measured value (if baseline > 60%) ○ < 55% of

absolute measured value (if baseline > 55%) ○ < 50% of

absolute measured value (if baseline > 50%) ○ < 45% of

absolute measured value (if baseline > 45%) ○ < 40% of

absolute measured value ○ < 35% of absolute measured value

○ < 30% of absolute measured value

○ < 25% of absolute measured value ○ < 20% of absolute

measured value

● Area under the curve for cumulative, high and low postoperative values outside of preestablished, individualized patient blood pressure goals based upon preoperatively observed blood pressure values as well as values clinically accepted to provide adequate organ perfusion. This analysis will be performed for systolic, diastolic and mean arterial pressures (AUCSBP-hi, AUCSBP-low, AUCSBP-cum, AUCDBP-hi, AUCDBP-low, AUCDBP-cum, AUCMAP-hi, AUCMAP-low, AUCMAP-cum). All postoperative blood pressure data will be collected with either invasive arterial catheterization [Q30 secs] or non-invasive blood pressure monitoring [Q15 min] as determined by the attending anesthesiologist caring for the subject in the PACU.

● Area under the curve of postoperative progressive categorical pulse oximetry (SpO2) desaturations (AUCSpO2) including the following:

○ AUCSpO2 < 95% regardless of intraoperative FiO2 values ○

AUCSpO2 < 90% regardless of intraoperative FiO2 values ○

AUCSpO2 < 85% regardless of intraoperative FiO2 values ○

AUCSpO2 < 80% regardless of intraoperative FiO2 values ○

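### Postoperative AUCs are accumulated over unequal monitoring windows (PACU stay or 12 ICU hours), so they can appear associated with outcome when desaturation has no effect

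*Combined protocol and SAP*

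**What the plan says.** The Synopsis (Duration of Treatment) has monitoring "continue through the surgery to either PACU discharge or the initial 12 hours of post surgical ICU treatment". Section 7.2.3 gives the same rule: the period runs "to PACU discharge or if the subject goes to the ICU through the first 12 hours of ICU admission". Section 7.4.1 treats the two windows as one set of "postoperative (PACU or initial 12 hours of the ICU stay) parameters".

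Section 7.4.1.2 lists the postoperative AUCs separately from the intraoperative ones in 7.4.1.1. They comprise rSO2 areas below a series of thresholds, SpO2 areas below a series of thresholds, and, for blood pressure, "Area under the curve for cumulative, high and low postoperative values outside of preestablished, individualized patient blood pressure goals". None is divided by monitored time or limited to a window shared by all subjects. Urine output, in the same lists, is defined per kg per hour.

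The Synopsis and section 6.4 plan logistic regressions of detrimental outcomes on rSO2 AUC and on blood pressure AUC. SpO2 AUC is not named there, but the Study Rationale intends to correlate it with outcomes as well. Section 15 specifies forward stepwise logistic regression at p < 0.05. It names no exposure-time term, no offset and no stratification by PACU or ICU. The composite in 7.4.1.2 counts, among other components, a PACU stay of 2 hours or more, a hospital stay of 4.5 days or more, and postoperative need for inotropes or vasoactive drugs.

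**The concern.** An area under a threshold grows with the time over which it is collected. Here that time is set by events after surgery: how long the subject stays in PACU, and whether the subject goes to ICU. Both are linked to the outcomes being predicted.

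There are two routes to a spurious association. First, ICU subjects contribute 12 hours where PACU subjects contribute far less; if ICU subjects also have more complications, AUC tracks outcome through destination alone. Second, among PACU subjects, a longer stay both enlarges the AUC and, at 2 hours, scores as a composite event.

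The pilot exists to choose endpoints and design for a multicenter trial. A threshold or AUC picked because it stood in for monitoring time would be carried into that trial.

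**Working it through.** The plan gives no figure to reproduce: it states no power, event rate or expected PACU stay.

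**Inputs from the documents.** N = 100; ICU window 12 h; at least 10 to 20 ICU subjects expected per 100 (ICU length-of-stay item, 7.4.1.2); test level 0.05; a 2 h PACU cut-off in the composite.

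**Assumptions.** Mean PACU stay 1 to 3 h; all event rates; the distribution of desaturation.

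**Step 1: ratio of windows.** If hourly burden is r and monitored time is T, then postoperative AUC = r × T. At equal r, the ICU-to-PACU ratio is 12 / T(PACU):
- 1 h: 12/1 = 12
- 2 h: 12/2 = 6
- 3 h: 12/3 = 4

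**Step 2: ICU route.** Simulation with 3,000 trials per scenario and N = 100. ICU subjects have 12 h; PACU subjects have a mean of 2 h (±40%). Hourly burden has the same distribution in both groups and no effect on outcome. PACU risk is 20%. Each trial applies a one-covariate logistic likelihood-ratio test at 0.05. Percentage of trials in which unscaled AUC was significant:

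| ICU subjects | ICU risk 20% | ICU risk 40% | ICU risk 60% |
|---|---|---|---|
| 10 | 6.8 | 13.6 | 32.0 |
| 15 | 6.0 | 15.9 | 42.2 |
| 20 | 6.5 | 17.0 | 49.0 |

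With 15 ICU subjects and 60% v 20% risk, a 1 h PACU mean gives 51.4% and a 3 h mean gives 32.5%. Over all these scenarios AUC per hour gave 4% to 6%, and AUC over a common early window gave 5% to 7%. At equal risk the per-hour version gave 5.7%, 5.8% and 6.2%, so most of the 6% to 7% in the first column belongs to the test and not to exposure time.

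A second set of simulations used a lognormal hourly burden, a rank-sum test, and event rates of 60–90% (ICU) v 30–40% (PACU). Unscaled false positives ran from about 8% to about 80%; repeat runs put the lower end at 7–8% and the upper end at 76–81%. The low end is 10 ICU subjects at 60% v 40%; the high end is 20 at 90% v 30%.

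**Step 3: PACU route, no ICU subjects.** The outcome is a PACU stay of 2 h or more, or an unrelated event. Cumulative AUC was falsely associated in 27–38% of trials in one set of assumptions. In another (mean stay 1.5–2 h, unrelated event rate 20–40%) it was 20–99%, with AUC per hour at 4–6%.

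**Step 4: does dividing by time cure it?** Only if desaturation accrues evenly. When the burden was placed early after surgery, AUC per hour was falsely associated in 6–78% of trials, because division by 12 h dilutes ICU subjects. Cumulative AUC then stayed at 4–5%. The common early window stayed near 5% under both patterns.

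**The case against.** The strongest reply is that the AUC-outcome regressions are exploratory, in a pilot, and that total exposure is a legitimate measure: the Study Rationale cites an effect of even a few minutes below an absolute threshold. Times in PACU and ICU are collected, so an analyst could adjust. It can also be said that the postoperative rSO2 item omits the word used in the intraoperative item ("Area under the curve of cumulative rSO 2 desaturations"), and that in the blood pressure item the word may only label one of three variants.

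Part of this stands. The Synopsis and section 6.4 do list these regressions as exploratory, and the Synopsis (Criteria for Evaluation) frames the primary endpoint around the randomized comparison. Section 7.4.1, however, calls the relationship between oximetry data and clinical variables the primary endpoint, so the label does not settle the matter. An AUC with no stated denominator or window is a total, whatever adjective precedes it. Total dose deserves reporting, but it cannot be separated from destination when one group is observed for 12 hours. That adjustment is possible does not make it planned.

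The size is also sensitive to the shape of the data. When 70% of subjects were assigned zero AUC regardless of monitoring time, as might happen at the extreme thresholds, cumulative AUC gave only 5–6% false positives. The artefact belongs chiefly to thresholds that many subjects cross.

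A reader might infer that every AUC in the plan is distorted by the 12-hour ICU window. The documents do not support that: intraoperative AUCs are separate endpoints that contain no ICU hours, although they too are unscaled and grow with operating time.

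A reader might also infer that the comparison of arms is biased. Absent an intervention effect on PACU stay or ICU use, monitoring time has the same distribution in both arms and the rank-sum test remains valid. With 10 to 20 ICU subjects, a split differing by 4 or more has probability 26–45%, but that is chance variation the test already allows for.

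**Conclusion.** The concern holds for the postoperative AUCs in the AUC-outcome models. Followed as written, the plan can produce an association between postoperative AUC and outcome when desaturation has no effect.

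The range of roughly 8% to 80% against a nominal 5% rests on PACU stays and event rates that the documents do not give, so it shows what is possible and is not a forecast. The ICU route requires worse outcomes in ICU subjects. That is plausible given the vasoactive-drug and hospital-stay components of the composite, but it is not stated. The PACU route needs no ICU subjects, only an outcome that includes PACU stay.

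It would be tempting to conclude that AUC per monitored hour is the correct variable. It is not safe as the main one: it reverses the artefact if desaturation is concentrated early, and the documents do not say how desaturation is distributed over the postoperative period. No choice of scale removes confounding if ICU subjects truly desaturate more per hour.

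**What to change.** For the AUC-outcome models, define the main postoperative AUC as the area over an early window common to PACU and ICU subjects. Choose its length so that essentially all subjects are monitored throughout it, from pooled monitoring durations and without reference to arm or outcome. One hour may be too long: the Aldrete item in 7.4.1.2 allows the 60-minute score to be taken at discharge instead.

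Report cumulative AUC and AUC per monitored hour as sensitivity analyses, with PACU/ICU destination forced into the model. Destination arises after randomization, so this adjustment belongs in the association models and not in the comparison of arms. Keep intraoperative and postoperative AUCs separate, as the plan already does.

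The cost is a few lines in 7.4.1.2 and section 15 plus some recoding. No new data are needed: the oximeter stores its readings, its clock is synchronized with the anesthesia record (11.3.2), and time in PACU/ICU is collected (11.3.3.2). The small downside is that later ICU data drop out of the main predictor; the cumulative sensitivity analysis keeps them in view.

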**Criteria for Evaluation:**

A large number of intraoperative and postoperative clinical variables that include cerebral oximetry, pulse oximetry, blood pressure, a composite outcome measure and clinical variables representing organ function will be assessed with the primary endpoint being the determination of which clinical variables are improved, if any, as a result of being randomized to open NIRS data monitoring with a predefined desaturation intervention algorithm guideline. The Mini Mental Status exam and Confusion Assessment Method test will be used to determine if any measured clinical variables have an effect upon neuropsychological outcomes. The frequency and effectiveness of the various cerebral desaturation mitigating interventions will be assessed in the intervention cohort.

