### **6.2 Primary Objective**

The primary objective of this pilot study is to identify the most relevant clinical outcome variables which significantly diverge as a result of being randomized to the intervention cohort vs. the control cohort so that a larger, multicenter, prospective, randomized controlled clinical trial can be designed to further test the primary hypothesis as stated in the preceding section. The subsequent larger, multicenter trial will be conducted to definitively demonstrate the ability of INVOS® 5100 guided NIRS-based bi-frontal monitoring to improve clinical outcomes in this surgical patient group and potentially establish a new U.S. Food and Drug Administration cleared indication for this monitoring modality.

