### **10.3 Intervention Group**

The intervention group will have baseline NIRS values obtained in a manner analogous to the control group. Following recording of the baseline values the subjects will be induced into general anesthesia and the clinicians as well as an IRB registered research assistant will be able to openly monitor the NIRS data. Upon observed cerebral desaturations greater than 20% of the oxygen supplemented baseline on either frontal hemisphere the research assistant will inform the anesthesia clinician that a significant cerebral desaturation is occurring and requires treatment. At this point a standardized interventional protocol will be followed that is detailed in Appendix C. The clinicians caring for the subject will have the ability to override the study intervention algorithm based upon the patient's physical condition at the time.

The intervention protocol for observed desaturations >20% will involve insuring that the subject's head vessels are not kinked or obstructed, increasing the mean arterial pressure via an intravenous fluid bolus or administration of a vasoconstrictor (i.e. phenylephrine or ephedrine) as deemed appropriate by the anesthesia clinician caring for the subject, normalizing PaCO2 to a value between 40 to 50 mmHg, or alternatively normalizing end tidal CO2 to a value of 35 to 45 mmHg. Subsequent interventions may include increasing the FiO2, especially if the SpO2 is below 98% or administering an intravenous inotropic agent if a low flow state is suspected. Administration of an inotrope will occur as judged by the clinician caring for the subject. Finally, in cases where the subject's hematocrit is known or suspected to critically low transfusion of allogeneic blood will be considered. The decision to transfuse allogeneic blood will be made by the anesthesia and surgery clinicians caring for the subject.

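### The primary endpoint counts rSO2, blood pressure and SpO2 traces as clinical variables that may improve, in conflict with the hypothesis; differences in them, above all in rSO2, show that the algorithm was delivered, not clinical benefit

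*Combined protocol and SAP*

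**What the plan says.** The synopsis, under Criteria for Evaluation, lists "clinical variables that include cerebral oximetry, pulse oximetry, blood pressure, a composite outcome measure and clinical variables representing organ function" and, later in the same sentence, states the endpoint as follows: "primary endpoint being the determination of which clinical variables are improved, if any, as a result of being randomized to open NIRS data monitoring". Nothing in that sentence sets the monitor readings apart from patient outcomes.

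Section 7.4.1 gives another definition: "The relationship between the observed cerebral oximetry data and a number of predefined intraoperative and postoperative clinical variables will serve as the primary endpoints". It continues: "The clinical variables will include the following intraoperative and postoperative (PACU or initial 12 hours of the ICU stay) parameters". The first entry in 7.4.1.1 is "Area under the curve of cumulative rSO 2 desaturations". Blood pressure AUCs follow ("This analysis will be performed for systolic, diastolic and mean arterial pressures"), then SpO2 AUCs. Section 7.4.1.2 repeats all three for the postoperative period. Section 11.3.1 says again that the variables collected in this period are the primary endpoints.

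The hypothesis in 6.1 is worded on postoperative clinical outcome measures. The objective in 6.2 is to "identify the most relevant clinical outcome variables which significantly diverge" between the arms, so that the next trial can be designed.

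In 10.3, a fall in rSO2 is what calls for treatment. The responses include "increasing the mean arterial pressure via an intravenous fluid bolus or administration of a vasoconstrictor" and, possibly later, a higher FiO2, especially when SpO2 is below 98%. Sections 8.6, 10.2 and 11.2.4.3 hide the rSO2 display in the control group.

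**The concern.** A primary endpoint should be something that can change only if patients fare better or worse. rSO2 is the signal that the intervention acts on, and only one arm's clinicians can see it. If they respond to it as planned, rSO2 should differ between arms whether or not any patient benefits. Such a difference is a useful check on delivery. Under the synopsis wording, however, it can be reported as a clinical variable improved by randomisation, that is, as a primary-endpoint finding.

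The purpose of the pilot makes this matter. Its results are meant to choose endpoints for a definitive multicentre trial and possibly to lead to a new cleared indication (6.2). A report that leads with improved AUCs would describe what the algorithm did to the monitor, under a heading that readers take to mean patient benefit.

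**Working it through.** The plan gives no effect size, SD or power, so it has no figure of its own to reproduce. The check is mainly a comparison of sections.

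1. **How closely each trace is tied to the algorithm.**
   - rSO2 is the trigger (10.3) and is hidden only in controls, so the link is strong. The trigger is stated differently in 7.1 and 10.3 (more than 20% below the oxygen-supplemented baseline) and in 7.2.3 (at least 10% against the room-air baseline). Those sections must be reconciled, but in each of them the trigger is rSO2.
   - Mean arterial pressure is a direct lever (10.3). The BP AUCs are taken above goal, below goal and cumulatively, so raising pressure could shrink one and enlarge another.
   - SpO2 is affected only indirectly, through an FiO2 step that may or may not be taken.

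2. **Roles given to the same quantity.** Desaturation and AUC rSO2 appear as primary endpoints (7.4.1), as secondary objectives 1 and 3 (6.3), and as predictors of outcome (6.4). AUC BP is both a primary endpoint and a predictor. No section ranks these roles.

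3. **Self-reference.** Section 7.4.1 makes the primary endpoint the relation of oximetry data to a list whose first entry is AUC rSO2. That entry relates rSO2 to itself.

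4. **Count.** Trace bullets: 3 per period × 2 periods = 6. Other bullets: 16 intraoperative + 28 postoperative = 44. The traces are 6 of 50 bullets (12%). Expanded by threshold and baseline, each period holds 8 × 2 + 9 = 25 rSO2 AUCs, 9 BP AUCs and 6 SpO2 AUCs: 40 per period, 80 in all.

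5. **Illustrative chance that one trace AUC differs significantly.** Inputs: 50 per arm (100 randomised 1:1) and the Wilcoxon rank-sum test (section 15). Assumed: two-sided 0.05, a normal shift of d SD, and Wilcoxon efficiency 3/π.
   - Effective n per arm = 50 × 3/π = 47.7; power ≈ Φ(d × √(47.7/2) − 1.96) = Φ(4.886d − 1.96).
   - d = 0.3: Φ(1.47 − 1.96) = 0.31.
   - d = 0.5: Φ(2.44 − 1.96) = 0.69.
   - d = 0.8: Φ(3.91 − 1.96) = 0.97.

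   The shifts are not from the documents. The normal-shift model fits poorly at deep thresholds (rSO2 below 20%, SpO2 below 70%), where many AUCs may be zero.

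6. **Other algorithm actions in the list.** Vasopressor/inotrope use (2 bullets), crystalloid and colloid volumes (2), red-cell transfusion (3) and desaturation-prompted change in surgery (1) make 8 bullets. They are responses that 10.3 describes or direct consequences of seeing a desaturation. The composite in 7.4.1.2 also counts postoperative inotropes or vasoactive drugs. No direction of benefit is defined for any of these.

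**The case against.** The strongest defence is that 6.1 and 6.2 already confine the hypothesis and the choice of future endpoints to clinical outcomes. A reader might infer from the endpoint list that the pilot could confirm clinical benefit, or nominate endpoints, on monitor traces alone. The documents do not support that: a trace change would not satisfy the hypothesis as worded, and no success rule exists to be met. This part of the defence stands. What it leaves is a primary endpoint that conflicts with the hypothesis it is meant to serve.

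Other strong readings also fail:

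- **All three traces are equally driven.** They are not. No section hides blood pressure or SpO2 from control-arm clinicians, the BP AUCs run in both directions, the FiO2 step is optional, and clinicians may override the algorithm. The argument is firm for rSO2, weaker for blood pressure and weakest for SpO2.
- **The intervention arm is treated until rSO2 recovers.** Section 10.3 gives a trigger and responses, not an end point for treatment.
- **About two thirds of the list is monitor output (80 of 124).** That figure expands the trace bullets by threshold, baseline and period but counts every other bullet once, although several of those also hold more than one measure (Aldrete, MMSE, CAM, renal function).
- **A significant difference is nearly certain.** That depends on the assumed shift; at 0.3 SD the power for one AUC is only about 31%.

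It can also be said that this is a hypothesis-generating pilot. That lowers the stakes for any single p-value, but choosing endpoints is the pilot's stated purpose.

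**Conclusion.** The concern holds as a conflict of definition. Followed as written, the synopsis, 7.4.1 and 11.3.1 allow a between-arm difference in rSO2, and less directly in blood pressure or SpO2, to be reported as a primary-endpoint improvement. Such a difference would show that the algorithm was delivered; it would not show that patients benefited. Six of 50 listed bullets are affected, and 8 more describe treatments or actions linked to the algorithm.

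This conclusion rests on the wording of the sections. The power figures only illustrate it: a moderate rSO2 shift of 0.5 SD, if it occurred, would reach significance on one AUC about 69% of the time with no effect on any outcome. The documents give no basis for saying how large the shift will be.

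**What to change.** In the synopsis (Criteria for Evaluation), 7.4.1 and 11.3.1, before the data are analysed:

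- Move the rSO2, SpO2 and BP AUCs to a process/delivery list, together with vasopressor/inotrope use, fluid volumes, transfusion and desaturation-prompted change in surgery. Still report them by arm, and keep them as exposures in the regressions.
- State that only individually named patient outcomes, each with a direction of benefit, can support the primary hypothesis or be nominated for the next trial. Name them one by one, not by section. Limiting the list to 7.4.1.2 would lose the intraoperative stroke/TIA, myocardial ischaemia/infarction and atrial fibrillation outcomes in 7.4.1.1.
- Report the composite also without its inotrope/vasoactive-drug component.
- Use one definition of the primary endpoint in the synopsis and in 7.4.1.

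The cost is rewording and a shorter headline list; no data or analysis is lost. Multiplicity is not solved. Moving 6 + 8 bullets leaves 50 − 14 = 36. At one test each at 0.05, about 36 × 0.05 = 1.8 chance findings would be expected if nothing differed, and if the tests were independent the chance of at least one would be 1 − 0.95^36 = 0.84. Some of the 36, such as the procedure performed and time on single lung ventilation, describe the operation and are not outcomes, so the named list should be shorter still.
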